#### **5.1.1.2. Analysis Scope**

The analysis of safety will include safety data collected from the beginning of the study until study site approval of PA7 for each participant. The vaccination groups that will be presented are: placebo, Ad26.COV2.S, non-mRNA (any number of doses) + Ad26.COV2.S booster or mRNA (any number of doses) + Ad26.COV2.S booster, and mixed schedule group. The safety data will be presented in three separate layouts: layout 1a covers the safety data after Ad26.COV2.S and placebo only, up until receipt of another COVID-19 vaccine; layout 1b covers the safety data after Ad26.COV2.S when given as a booster on top of mRNA vaccinations or on top of non-mRNA vaccinations, layout 2 covers all other safety data after outside vaccinations or any other order

mixing outside vaccination with Ad26.COV2.S vaccination (eg: Ad26.COV2.S + mRNA vaccination).

The efficacy analysis planned for the open-label active phase, comparing the different study cohorts, will include efficacy data from the date of unblinding up to 30 days prior to study site approval of PA7. This 30 day window is chosen to assure that the active surveillance took place for the full duration of the COVID-19 episode and no symptoms would be missed. A separate listing will be provided to include the COVID-19 events within 30 days prior to study site approval of PA7. There are 3 study cohorts: one dose schedule; two-dose schedule and booster dose schedule. These cohorts are described in more detail in Section [5.2.1](#).

### **5.1.2. Scope of the Analysis of the Open-Label Passive Follow-up Phase**

After implementation of PA7, the active follow-up of suspected COVID-19 is replaced by a passive follow-up (from study site approval of PA7 up to end of study).

The safety data of the open-label passive follow-up phase will be presented similarly as for the open-label active phase, however the data will be presented separately. All data collected during the study from study site approval of PA7 until study end will be included.

For efficacy in the open-label passive follow-up phase, the COVID-19 events are based on the reporting of adverse events. The COVID-19 events will be summarized descriptively for the 1 dose schedule, 2 dose schedule and the booster dose schedule.

### **5.1.3. Participant Dispositions**

Participant information will be shown for the full analysis set by randomized treatment group and by the vaccination groups used in the safety analysis, presented in Section [5.4.4](#).

The number of participants in the following disposition categories will be summarized throughout the study by vaccination group and overall:

- participants in the FAS
- participants in the FAS7
- participants randomized
- participants vaccinated at day 1 and not randomized
- participants randomized, not vaccinated at day 1
- participants randomized and vaccinated at day 1
- participants vaccinated at day 1 with incorrect treatment
- participants vaccinated at day 1 with correct treatment
- participants who discontinued study (and reasons for discontinuation)
- participants who discontinued study before PA7 site approval

Additionally, the disposition of the efficacy risk sets (explained in Section 5.2.2) will be provided including the reasons why subjects are excluded from the risk set starting from the initial study vaccination received in the FAS. The efficacy risk set will be presented for the 1 dose cohort, 2 dose cohort and booster dose cohort. Note that subjects from the 1 dose cohort can also be included in the 2 dose or booster dose cohort and therefore can be part of multiple risk sets.

## 5.2. Efficacy Analysis of the Open-Label Active Follow-up Phase

Note that no hypothesis testing and no efficacy evaluations will be performed. All endpoints will be evaluated using descriptive statistics. These descriptive summaries can not support any comparisons between groups or any interpretation regarding difference between groups.

The efficacy analyses will be based on a subset of the participants of the FAS, ie the participants who are at risk to develop an endpoint in the open-label active phase. These subsets are called risk sets and depend on the vaccination schedule the participants received as indicated in Table 5 and explained in Sections 5.2.1 and Section 5.2.2.

As only the data under the open-label active follow-up is considered, an observational period is defined for each of the vaccination groups (Table 5 and explained in Section 5.2.3). Only the efficacy data within this observational period will be summarized. Efficacy endpoints for the vaccination groups outside of this observational period, ie within 30 days prior to the PA7 site approval, will be listed.

**Table 5: Risk set and observational period**

Risk set	Start of observational period	Censoring End of observational period	Inclusion criteria	Exclusion criteria
One dose cohort	Maximum of 
 
• Unblinding date
 
• First dose of Ad26.COV2.S
 
	Minimum of 
 
• Endpoint observed
 
• Outside vaccination
 
• Second Ad26.COV2.S vaccination
 
• Discontinuation
 
• PA7 site approval – 30 days
 
	At least 1 dose of Ad26.COV2.S prior to PA7 site approval – 30 days and prior to study discontinuation	Prior to the observational period 
 
• SARS-CoV-2 infection
 
• Discontinued
 
• Outside vaccination
 

Two dose cohort	Maximum of 
 
• Unblinding date
 
• Second dose of Ad26.COV2.S
 
	Minimum of 
 
• Endpoint observed
 
• Outside vaccination
 
• Third Ad26.COV2.S vaccination
 
• Discontinuation
 
	At least 2 doses of Ad26.COV2.S prior to PA7 site approval – 30 days and prior to study discontinuation	Prior to observational period 
 
• SARS-CoV-2 infection
 
• Discontinued
 
• Outside vaccination
 
• More than 70 days between first and second dose
 

**Table 5: Risk set and observational period**

Risk set	Start of observational period	Censoring End of observational period	Inclusion criteria	Exclusion criteria
		
 
PA7 site approval – 30 days
 
		Ad26.COV2.S vaccination
Booster dose cohort	Maximum of 
 
Unblinding date
 
Second dose of Ad26.COV2.S
 
	Minimum of 
 
Endpoint observed
 
Outside vaccination
 
Third Ad26.COV2.S vaccination
 
Discontinuation
 
PA7 site approval – 30 days
 
	At least 2 doses of Ad26.COV2.S prior to PA7 site approval – 30 days and prior to study discontinuation	Prior to observational period 
 
SARS-CoV-2 infection
 
Discontinued
 
Outside vaccination
 
70 days or less between first and second Ad26.COV2.S vaccination
 

### 5.2.1. Study dose cohorts

Participants will be allocated to the study dose cohorts, if they are part of the risk sets and if they have follow-up time within the observational period, as follows:

- One-dose schedule cohort: participants who only received a single dose of the Ad26.COV2.S vaccination. Participants who received a further Ad26.COV2.S vaccination remain in this cohort until they received their second vaccination.
- Two-dose schedule cohort: participants who received two doses of the Ad26.COV2.S vaccination with a maximum gap between doses of 70 days.
- Booster dose schedule cohort: participants who received two doses of the Ad26.COV2.S vaccination with a minimum gap between doses of 71 days.

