On 27 February 2021, the US Food and Drug Administration (FDA) issued an EUA for the Ad26.COV2.S vaccine for the prevention of coronavirus disease 2019 (COVID-19). On 11 March 2021, the European Commission granted conditional marketing authorization for the Ad26.COV2.S vaccine. Additionally the World Health Organization granted Ad26.COV2.S vaccine emergency use listing on 12 March 2021. Other regulatory agencies have subsequently authorized or (conditionally) approved the vaccine. On 20 October 2021, the FDA amended the EUA for Ad26.COV2.S to authorize the vaccine as homologous or heterologous booster. On 16 December 2021, the European Commission authorized (as part of the conditional marketing authorization) Ad26.COV2.S as homologous booster or as heterologous booster following completion of primary vaccination with an approved mRNA COVID-19 vaccine in individuals 18 years of age or older. The European commission approved on January 9th 2023 Ad26.COV2.S fully, ie no longer a conditional approval. The vaccine has received authorization of use in over 100 countries, the clinical development program has moved from 'Development' to a 'Life cycle management' phase. Hence the scope and the extent of the open-label analysis has been reduced. For the open-label phase, the safety, immunogenicity, and efficacy endpoints following cross-over and/or booster vaccination will be descriptively summarized by study cohort. Relative vaccine efficacy will not be assessed during the open-label phase. Results will be presented as incidence rates per study cohort (eg incidence of moderate to severe molecularly confirmed COVID-19).

From 8 July 2022, suspected COVID-19 events were no longer sent to the Clinical Severity Adjudication Committee (CSAC) for assessment and sequencing of cases was stopped on 4 July 2022. Since the implementation of Protocol Amendment 7 (PA7) dated 27 April 2022, at sites where the protocol is approved, there is a passive follow-up of COVID-19 episodes.

With PA7 the open-label phase is divided into two parts:

1. Active follow-up of suspected COVID-19 episodes (according to the initial design of the study, from unblinding up to the date the study site approves PA7)
2. After implementation of PA7, the active follow-up of suspected COVID-19 is replaced by a passive follow-up (from study site approval of PA7 up to end of study).

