**Table 2: Vaccination Schedule VAC31518COV3009 - Open-label Phase**

Group	N*	Day 1	Day 57	Unscheduled Unblinding Visit**/ Day 1 for newly enrolled participants***	Booster Vaccination Preferably Vac 1 + 6-12 months Minimally Vac 1 + 3 months****
1	Approx. 15,000	Ad26.COV2.S ( $5 \times 10^{10}$ vp)	Ad26.COV2.S ( $5 \times 10^{10}$ vp)		Ad26.COV2.S
2	Approx. 15,000	Placebo***	Placebo****	Ad26.COV2.S ( $5 \times 10^{10}$ vp)	

N = number of participants; vp = virus particles.

Note: It is intended that a minimum of approximately 30% of recruited participants will be  $\geq 60$  years of age and approximately 20% of recruited participants will be  $\geq 18$  to  $<40$  years of age.

\* It is possible that there might be over enrollment of participants in this study.

\*\* All participants will be unblinded (informed whether they received placebo or Ad26.COV2.S) at the on-site or remote unblinding visit following EUA in the US and approval of Protocol Amendment 4 by the local Health Authority and the IEC/IRB, and the study will continue as an open-label study. Participants who were in the placebo arm will be offered to receive a single dose of Ad26.COV2.S  $5 \times 10^{10}$  vp. After the study pause, the unblinding visit should be scheduled as soon as reasonably practicable and preferably no later than 2 months following local approvals of Protocol Amendment 5 have been received. The unblinding visit may be combined with the next planned study visit, if appropriate.

\*\*\* The newly enrolled participants will be randomized to Group 1 (to receive two doses of Ad26.COV2.S) or to Group 2 (to receive one dose of Ad26.COV2.S on Day 1 instead of 2 doses of placebo. (There will be no administration of placebo on Day 57).

\*\*\*\* Vaccination at Day 57 is not applicable for participants who were unblinded after the placebo vaccination at Day 1 and prior to receiving the second placebo vaccination.

\*\*\*\*\*Following implementation of Protocol Amendment 6, all ongoing eligible participants who received only 1 Ad26.COV2.S vaccination in the study will be offered 1 Ad26.COV2.S booster vaccination. Participants who already received 2 vaccinations with Ad26.COV2.S at the  $5 \times 10^{10}$  vp dose level or any COVID-19 vaccinations outside of the study (including the Janssen vaccine) at the time of local approval of Protocol Amendment 6 are not eligible to receive a booster vaccination with Ad26.COV2.S.

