For safety, the data of the double-blind phase and the open-label active follow-up phase are combined. Safety data for the following vaccination groups will be presented:

1. Placebo: Participants who were randomized and first vaccinated with Placebo until they received any other active COVID-19 vaccine.
2. Ad26.COV2.S: Participants whose first active vaccination is Ad26.COV2.S. Participants remain in this group (also when receiving a second dose of Ad26.COV2.S) until they receive an outside active COVID-19 vaccination.
3. Any schedule non-mRNA + Ad26.COV2.S OR any schedule mRNA + Ad26.COV2.S: Participants who first received one or more active non-mRNA COVID-19 vaccinations or one or more active mRNA COVID-19 vaccinations and who were boosted with one or more Ad26.COV2.S vaccinations
4. Mixed achedule: all other safety data and safety follow-up, including safety data following only an outside vaccine regimen, or safety data following a mixed schedule of Ad26.COV2.S and mRNA/non-mRNA vaccines.

For efficacy, the open-label phase will include 3 main study cohorts, based on the vaccination schedules received:

- Two-dose schedule cohort: participants who received the 2 doses of the Ad26.COV2.S vaccine according to initial design of the study on Day 1 and Day 57 (Visit 1 and Visit 4), regardless whether this was before or after unblinding. The number of days between

first Ad26.COV2.S vaccination and second Ad26.COV2.S vaccination must be a maximum of 70 days to qualify for the two-dose cohort.

- One-dose schedule cohort: participants who received a single dose of the Ad26.COV2.S vaccine in the context of the open-label vaccination (eg, placebo participants receiving Ad26.COV2.S vaccine during cross-over vaccination) or participants who only received one dose of Ad26.COV2.S vaccine during the double-blind phase of the study. These participants remain in this cohort until they receive the booster vaccination in the context of PA6 or an outside vaccination. Participants who will not receive a booster dose will continue in this cohort until they receive an outside vaccination.

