- Booster dose schedule cohort: participants who, during the course of the study, have received only a single dose of the Ad26.COV2.S vaccine and received a booster vaccination under PA6, preferably within 6 to 12 months after the initial vaccination, with a minimum of 3 months after the initial vaccination with Ad26.COV2.S. The number of days between first Ad26.COV2.S vaccination and second Ad26.COV2.S vaccination must be a minimum of 71 days to qualify for the booster dose cohort.

With PA7, requirements for COVID-19 episode reporting are changed, ie, a passive surveillance approach is adopted, defined as following up on new COVID-19 episodes during scheduled phone calls with the participants. Participants will enter this phase on the date of site approval of PA7. The data collected in the passive follow-up phase will be analyzed separately from the open-label active follow-up phase and the efficacy analysis will be described in a separate section within this SAP. For efficacy the same study cohorts as in the open-label active phase are used. Efficacy following a COVID-19 vaccination given outside of the study will not be assessed. The safety data after PA7 approval will also be presented separately from the safety data under the active follow-up. The same vaccination groups are used as for the open-label active follow-up phase.

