#### **5.4.4. Vaccination groups**

All safety analyses will be tabulated by vaccination group according to the *as treated* principle. The COVID-19 vaccinations received outside of the study are considered as well. Participants can be present in more than 1 vaccination group as described below. Safety data by vaccination group will be analyzed descriptively.

The following vaccination groups will be presented:

A. Layout 1a:

1. Placebo

All participants who received as first vaccination a placebo injection. All safety data will be reported here until the participant receives an active COVID-19 vaccination (Ad26.COV2.S or outside vaccination).

2. Ad26.COV2.S

All participants who received as first active COVID-19 vaccination Ad26.COV2.S until the participant receives an outside COVID-19 vaccination. This includes participants who initially received placebo and subsequently received Ad26.COV2.S, however only the safety data after the Ad26.COV2.S vaccination until the participant receives an outside

COVID-19 vaccination (if applicable) will be presented here. The safety data of participants who received 2 or more Ad26.COV2.S vaccinations will be presented by post-dose 1, post-dose 2, etc.

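### The operative booster-cohort rule drops the PA6 condition, so late scheduled second doses count as boosters in efficacy, and safety layout 1a pools homologous boosters with scheduled second doses

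*SAP*

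**What the plan says.** **Efficacy.** Section 1.2 describes the booster cohort as participants who had only one Ad26.COV2.S dose and "received a booster vaccination under PA6, preferably within 6 to 12 months after the initial vaccination, with a minimum of 3 months" after it. The same paragraph adds a gap of at least 71 days. The two-dose cohort in Section 1.2 is the Day 1 and Day 57 schedule, with a gap of at most 70 days.

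Section 5.2.1, which allocates participants for analysis, keeps only the gap. The two-dose cohort is "participants who received two doses of the Ad26.COV2.S vaccination with a maximum gap between doses of 70 days". The booster rule is "Booster dose schedule cohort: participants who received two doses of the Ad26.COV2.S vaccination with a minimum gap between doses of 71 days". In Table 5 the only exclusion specific to the booster risk set is "70 days or less between first and second Ad26.COV2.S vaccination". The estimand tables in Section 1.1 use the same 70/71-day cut, and Section 5.3 reuses the cohorts of 5.2.1 for the passive phase. None of these places mentions PA6 or the Booster Vaccination Visit.

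**Safety.** For the open-label phase, Section 1 states that "the safety, immunogenicity, and efficacy endpoints following cross-over and/or booster vaccination will be descriptively summarized by study cohort". Section 5.4.4 instead forms one group of everyone whose first active vaccine was Ad26.COV2.S and says: "The safety data of participants who received 2 or more Ad26.COV2.S vaccinations will be presented by post-dose 1, post-dose 2, etc". Section 5.4.3 restarts the dose numbering at 1 when earlier injections were placebo only. Section 5.4 plans no subgroup presentations.

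**The concern.** A programmer will implement Section 5.2.1 and Table 5, not the description in Section 1.2. The two give different booster cohorts. Under the operative rule a participant on the original two-dose schedule whose second dose came late is reported as boosted. Yet Sections 1, 1.2 and 5.1.1.1 say that anyone who already had two doses at local PA6 approval is not eligible for a booster. Such a participant is ineligible for a booster and is analysed as having had one.

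What is at stake is the meaning of the booster-cohort incidence rates, including the summary of duration of protection after booster and the passive-phase rates. In safety, a reader looking for the event rate after a homologous booster will find only a post-dose 2 column that also contains the scheduled second doses of Group 1, which Table 2 puts at about 15,000 participants.

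**Working it through.** The SAP states no figure on this point, and the open-label phase has no sample size or hypothesis. The check applies the SAP's allocation rules to example cases.

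**Inputs.** Scheduled doses on Day 1 and Day 57 (Section 1.2). Cut at 70/71 days (Sections 1.1, 1.2, 5.2.1, Table 5). PA6 booster with a 3-month minimum (Section 1.2).

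**Step 1: lateness that changes the cohort.** Scheduled gap = 57 − 1 = 56 days. Tolerance = 70 − 56 = 14 days. A scheduled second dose 15 or more days late (gap of 71 days or more) moves to the booster cohort.

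**Step 2: 3 months in days.** Depending on the start date, three calendar months last from 89 days (28 + 31 + 30) to 92 days (31 + 31 + 30). Gaps of 71 to 88 days therefore qualify as booster in 5.2.1 while falling short of the minimum in 1.2.

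**Step 3: allocation under each text.**

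| Dose 2 | Gap (days) | Section 1.2 | Section 5.2.1 / Table 5 | Safety layout 1a |
|---|---|---|---|---|
| Scheduled | 56 or 70 | two-dose | two-dose | post-dose 2 |
| Scheduled, late | 71, 85 or 120 | neither | booster | post-dose 2 |
| PA6 booster | 92 or 240 | booster | booster | post-dose 2 |

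The texts disagree only in the middle row. On-time second doses are kept apart from boosters, and boosters that respect the 3-month minimum never enter the two-dose cohort.

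**Step 4: safety numbering.** A placebo participant's cross-over dose is post-dose 1 because numbering restarts, so a later PA6 booster is post-dose 2. A Group 1 participant's Day 57 dose is also post-dose 2. All three rows of the table share one column, and follow-up 2 inherits the same mixture.

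**Step 5: illustration only.** Let a share s of the pooled column come from source B, with B's rate twice that of the rest. The pooled rate relative to the rest is (1 − s) + 2s = 1 + s.
- Safety: if boosters made up 20% to 40% of post-dose 2, a true doubling after booster would show as 1.2 to 1.4.
- Efficacy: if late second doses made up 5% to 15% of booster person-time and had twice the PA6-booster rate, the reported rate would be 1.05 to 1.15 times the PA6-booster rate.

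The shares and the doubling are assumptions. The SAP does not bound them; Group 2, also about 15,000, could supply many boosters.

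**The case against.** The 70/71-day cut is a deliberate, non-overlapping, as-treated rule, and Section 1.2 contains it too. That is correct: the defect is not the cut itself but that the PA6 and 3-month conditions standing beside it in Section 1.2 are not carried forward.

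Section 5.1 says openly that safety and efficacy groups differ, and Section 1 says the open-label scope was reduced. So the safety grouping is intended. That does not remove the conflict with the statements in Section 1 that safety is summarised by study cohort.

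The month-by-month and calendar-time displays in Sections 5.2.4 and 5.2.5 would reveal booster person-time from before PA6. They help, but late second-dose participants can stay at risk alongside PA6 boosters afterwards, and there the displays cannot separate them.

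Several stronger readings are tempting but unsupported:
- *Every gap of 71 to 88 days is a late second dose.* The 3-month minimum is an instruction to sites; a booster given early as a deviation would fall in the same band.
- *The study pause delayed second doses.* The Table 2 footnote says only "After the study pause, the unblinding visit should be scheduled as soon as reasonably practicable". It concerns the unblinding visit and gives no pause length and no effect on second doses.
- *No planned table shows booster safety.* Layout 1b tabulates Ad26.COV2.S given after outside mRNA or non-mRNA vaccines. Only the homologous booster lacks its own summary.
- *PA6 was introduced to study booster safety.* The SAP says what PA6 offered, not why.

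**Conclusion.** The point holds and should be corrected. The operative efficacy rule classes any scheduled second dose given 71 or more days after the first as a booster, against the SAP's own description of that cohort. The contamination is one-way, provided that no PA6 booster was given within 70 days. The safety layout cannot show the homologous booster apart from the scheduled second dose.

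The size cannot be computed from the SAP: it depends on the number of late second doses and on the booster share of post-dose 2, neither of which is stated. The ratios above are illustrations, not estimates. There is no hypothesis, and Section 5.2 says the summaries cannot support comparisons between groups, so no test or efficacy claim is affected. What is affected is the label and reading of the cohort rates, which are the main efficacy output of this phase.

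**What to change.** 1. Reconcile Section 1.2 with Section 5.2.1, Table 5 and the estimand tables, and the safety statements in Section 1 with Section 5.4.4.
2. Derive one flag for each second Ad26.COV2.S dose from the dosing and visit record: scheduled second vaccination, or PA6 Booster Vaccination Visit. Use it in the active phase, the passive phase and safety.
3. Restrict the booster efficacy cohort to PA6 boosters. Show scheduled second doses with a gap of 71 days or more in a separate row, in neither main cohort, and report their number. State where a PA6 booster given earlier than Section 1.2 describes is counted.
4. Split the layout 1a post-dose 2 and follow-up 2 columns by the same flag. If the sponsor prefers the pooled layout, amend Section 1 so that it no longer says safety is summarised by study cohort, and state that homologous booster safety is not shown separately.

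The cost is SAP wording, one derived variable from data already collected, extra table columns and one extra row. The booster cohort shrinks by the number of late second doses. This concerns classification for analysis only; no dosing interval is proposed.
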